5.2. Secondary Outcomes

In addition to the indicators in the table above, we will examine other programmatic indicators available in TIER.Net, namely IPT initiation and completion, to sense possible indirect effects Project Unlocked has on the HIV programmatic services offered at the engaged facilities.

6. DATA MANAGEMENT

6.1. Data Sources

This study does not involve primary data collection. The study will utilize routinely collected programmatic data aggregated at the facility level for analysis. No additional primary data will be collected. No patient-level data will be accessed or otherwise used in this analysis. As such, there is no Personal Identifiable Information (PII) that will be included in this dataset.

Existing facility-level data will be abstracted from routine programmatic reports provided to Aurum, e.g., Quality Insurance (QI) reports reported on a monthly basis from TIER.Net. Data from these reports will be used to review study-associated outcomes to evaluate the impact of Project Unlocked on health facilities' HIV programs. To achieve this, data on key HIV indicators collected on a monthly basis from baseline (0 months) to 9 months post-intervention. Indicators will be compared between intervention and control facilities at key months (see Section 5). The key indicators that will be used in this analysis are described elsewhere (Section 5 and Table 3).

6.2. Data management

Monthly facility-level data for 10 months (baseline through 9 months) of key indicators along with facility-level characteristics at baseline (i.e., sub-district, facility size, treatment group), will be collated into a CSV file. Data will be abstracted from the routinely reported monthly, Excel-based reports into this dataset. After all data have been merged, the baseline dataset will be frozen and designated members of the study team will conduct data cleaning in R.

Structure of Dataset

The dataset will include one sheet and be in wide format (i.e., one row per facility). There will be one column per indicator of interest per month. There will be one row per facility, to enable easy aggregation of data collected per facility from months 4-9 of the intervention period. Data will be cleaned and organized in R.

Data entry validation

All data entry will be conducted under routine programmatic conditions. Program staff will use routine, existing facility-level protocols to enter and submit their data to Aurum and other entities. This study will not propose variations on this routine process (i.e., there is no data entry validation specific to this study). While one study member will collate the dataset from monthly reports, a secondary member will review the dataset to ensure quality of the final dataset. The dataset will be collated after the intervention period (i.e., at month 9). This will ensure that the most up-to-date data are captured in our analysis, and that the study team does not use the data to prospectively alter performance of the intervention.

Data cleaning

Study staff will review the routinely reported data for outliers and send inquiry to program staff on any outliers. Study staff will adjust any outliers in consultation with the facilities that generated the data.

Access to dataset

The dataset will be password protected and shared only with study and program staff.

Locking of database

The dataset will be cleaned in a standard statistical program (e.g., STATA or R). The dataset will be locked after all data have been merged and reviewed for outliers.

Information security

The dataset will be password protected and shared with the University of Washington through Aspera data transfer, a protected web portal for data sharing. All data are deidentified, containing only aggregated numbers at the facility level. Access to the database (data entry, reporting, and extraction) will be controlled by the study team. Study personnel requiring access to the database must will complete any required documentation and training required by Aurum prior to receiving access to the data.

Data ownership

All data will be owned by Aurum, but researchers with University of Washington will be primarily responsible for analysis, and thus will have access to it for cleaning and analytic purposes.

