3.5. Blinding

There will be no blinding in this study. Randomization will be conducted publicly with all clinic managers and district officials will be invited. Cooperation with program leaders is essential to maximize facility retention in the study.

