10.4 Performance monitoring

The investigator team will meet every two weeks to monitor performance of the study, with [name] (Aurum Unlock'd Joint Venture) and [name] (University of Washington) providing study updates on vital information, such as IRB timelines, status of protocol development, enrolment figures, and any issues/delays that the study might be experiencing.

II. TIMELINE

From start to finish, this study will last approximately two years, with the active study period occurring over nine months (Table 5). Study design and enrollment will occur in latter 2019. The intervention will be implemented from December 2019 through August 2020 (nine months). The first three months of the study period will be considered a run-in period, with the understanding that it will take time for the interns to be trained and fully integrated into the facilities where they work. Months 4-9 (six months) will be considered the "intervention period" and will be used in the analysis. This is depicted in Figure 3 below. Data cleaning and analysis will occur in Quarter 4 of 2020. Results will be ready for dissemination by mid-2021.

Figure 4. Time period for intervention and study period.

Table 5. GANTT chart for proposed study

	2019		2020				2021	
	Q3	Q4	Q1	Q2	Q3	Q4	Q1	Q2
Study Planning								
Protocol Development	Χ							
Community Engagement	Χ							
Enrollment		Х						
Randomization		X						
Implementation								
Learner training		X						
Run-in period		X	Χ					
Data collection			Χ	Х	Χ			
Analysis								
Data cleaning						Χ		
Data analysis						Χ		
Dissemination								
Write up							X	
Disseminate results								Х

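### Outlying outcome values may be adjusted by unblinded staff with unblinded facilities before lock, without limiting changes to confirmed errors or calling for an analysis of the as-reported data

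*Protocol*

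**What the plan says.** Protocol section 6.2 (Data management) sets out the cleaning step in two sentences: "Study staff will review the routinely reported data for outliers and send inquiry to program staff on any outliers", and then "Study staff will adjust any outliers in consultation with the facilities that generated the data".

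The surrounding text fixes who knows what, and when:

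- **Arm is in the file.** The monthly indicators and the "facility-level characteristics at baseline (i.e., sub-district, facility size, treatment group), will be collated into a CSV file" (section 6.2).
- **Arm is known.** "There will be no blinding in this study", and "Randomization will be conducted publicly with all clinic managers and district officials will be invited" (section 3.5).
- **All outcome months are visible.** Section 6.2 has the dataset put together only once the intervention period is over, at month 9. The Timeline section adds: "Data cleaning and analysis will occur in Quarter 4 of 2020".
- **Lock follows the adjustment.** "The dataset will be locked after all data have been merged and reviewed for outliers" (section 6.2).

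Section 6.2 also contains two partial safeguards. A file it calls the baseline dataset is frozen after merging and before cleaning in R, and a second team member reviews the dataset for quality.

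**The concern.** Querying odd values in routine data is proper. The difficulty lies in the instruction that follows the query. It provides for outliers to be adjusted and does not say that a value changes only when the source shows it was misreported. A facility that truly tests very few people, or truly loses many patients, is part of the outcome and should stay as reported.

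The people making the change can know the arm, have it in the file in front of them, and see the complete outcome series. The managers of the facilities they consult were invited to the public randomization. If decisions on which values to change, or how far, differ by arm even without intent, the comparison is biased. Each facility contributes one six-month summary to a t-test with 9-12 values per arm, so a single decision carries visible weight.

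**Working it through.** **1. Reproduce the plan's yardstick (Table 4).** Inputs from section 7.1: m = 1,687, cv = 0.596, p1 = 0.14, 5% level (taken as two-sided), 80% power, k = 12 or 9 per arm.

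Design effect = 1 + ((cv² + 1)m − 1) × ICC. At ICC 0.01 this is 1 + (1.3552 × 1,687 − 1) × 0.01 = 23.85. Effective n per arm = k × m / design effect = 12 × 1,687 / 23.85 ≈ 849, or 9 × 1,687 / 23.85 ≈ 637. Solving the two-proportion formula (pooled variance under the null) for p2:

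| k per arm | ICC 0.01 | ICC 0.03 | ICC 0.05 |
|---|---|---|---|
| 12, computed (stated) | 0.1905 (0.19) | 0.2300 (0.23) | 0.2591 (0.26) |
| 9, computed (stated) | 0.1989 (0.20) | 0.2455 (0.25) | 0.2800 (0.28) |

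All six cells reproduce. The detectable differences from 0.14 are about 5-6 points at ICC 0.01 and 12-14 points at ICC 0.05.

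**2. Spread between facilities (Table 1).**
- Testing (tested / headcount, 30 facilities with a readable headcount): mean 11.7%, SD 4.2 points, lowest 20/1,034 = 1.9%.
- Early default (early default / on ART, 31 facilities): mean 16.2%, SD 7.4 points, highest 335/828 = 40.5%.

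**3. Worst-case shift.** Replace the most extreme facility's whole value by the mean. Shift in the unweighted arm mean = (mean − extreme) / k. Standard error of the arm difference = SD × √(2/k).

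| Outcome | k = 12 | k = 9 | SE (k = 12 / 9) |
|---|---|---|---|
| Testing | (0.1166 − 0.0193)/12 = 0.8 points | /9 = 1.1 points | 1.7 / 2.0 points |
| Early default | (0.4046 − 0.1622)/12 = 2.0 points | /9 = 2.7 points | 3.0 / 3.5 points |

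One such decision is therefore worth about half a standard error for testing and 0.7-0.8 of one for early default.

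**4. A single month.** If monthly denominators are equal, changing one of six months has one sixth of the effect: about 0.14-0.18 points for testing (0.81/6, 1.08/6) and 0.34-0.45 points for early default (2.02/6, 2.69/6).

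**5. Does the direction of adjustment matter?** This was a simulation under no true effect: 40,000 draws, Table 1 testing values sampled without replacement, unweighted two-sample t-test. The adjustment patterns are assumptions.

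| Values moved to the mean | Bias, 9 / 12 per arm (points) | Type I error, 9 / 12 per arm |
|---|---|---|
| Most extreme, regardless of arm | about 0 | 5.1% / 5.0% |
| Lowest intervention facility only | 0.7 / 0.6 | 7.5% / 7.2% |
| Lowest intervention and highest control | 1.4 / 1.2 | 14.7% / 13.3% |
| Two lowest intervention and two highest control | 2.2 / 1.9 | 35.0% / 31.3% |

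Adjustment as such does no harm to the error rate. Adjustment that depends on arm does.

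**The case against.** The strongest defence is that this is ordinary query resolution. Outliers are queried first. The study sees no patient-level data (section 6.1), so asking the facility is the available route to the source. Both Table 1 extremes deserve a query: the facility at 40.5% early default shares its count of 335 with another facility, and the one at 1.9% tested averages 20 tests, 3 new positives and 6 initiations a month. Either could be a reporting error. This stands. The answer is to keep the query and limit what may follow from it.

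Several stronger readings are tempting but not supported:

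- **That the reported values are lost and changes could never be detected.** Section 6.2 freezes a file before cleaning, and the monthly reports already sit with the implementing partner. The name given to the frozen file is ambiguous, but the order of merge, freeze, clean suggests the raw values are kept.
- **That facilities have a stake in the result.** The protocol does not show this. Section 4.2 offers controls the programmatic interns at nine months, with no stated dependence on the findings.
- **That collating at month 9 is a fault.** Its stated purpose is current data and no feedback into the intervention, and any cleaning after the trial sees every month.
- **That a missing numeric threshold is a defect in itself.** It may stand in a statistical analysis plan that is not shown. The point here rests on the procedure that the protocol fixes.

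It is also fair to say that hiding one column masks only partly, since staff and facilities may remember a public allocation.

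**Conclusion.** The concern holds in a limited form. The protocol prescribes an arm-aware adjustment of outcome data before lock, does not confine it to confirmed errors, and does not call for the analysis that would show whether it mattered. The second reviewer is not described as masked, so that step does not remove the problem.

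The size is a possibility and not an estimate. The upper illustration is 0.8-1.1 points for testing and 2.0-2.7 points for early default, per facility moved. It assumes that a whole six-month value is replaced by the mean, equal weighting, and baseline spread like Table 1, whose early default figures come from one month (July 2019). The planned test is weighted, so actual shifts would differ. A reader might infer from the simulation that the trial's type I error is inflated to a particular level. The documents do not support that: the inflation appears only under assumed arm-directed changes, and arm-neutral correction leaves it at about 5%. The point should be addressed because the remedy is nearly free, not because bias is shown.

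**What to change.** Amend section 6.2 as follows:

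1. Keep the treatment-group column out of the cleaning file and merge it only after lock. State that this is partial masking.
2. Apply the same outlier flag to every facility and month; the threshold itself can be set in the statistical analysis plan.
3. Change a value only when the facility's source record or report confirms a reporting error. Otherwise keep the value as reported.
4. Log the old value, new value and reason for each change.
5. State that the frozen file is the unaltered as-reported data, and report the primary analysis on it as a sensitivity analysis.

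Cost: a few lines of text, one column withheld until lock, and one extra analysis run. Legitimate correction of routine-data errors is preserved, and the second team member already assigned to review the dataset can check the log.

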7. STATISTICAL CONSIDERATIONS

7.1. Sample size estimation

Sample size: We will enroll 18-24 clinics in this study, resulting in 9-12 clinics being in the treatment and the control arms of the study. The sample size is pre-determined by the number of available eligible clinics.

Study power: In Table 4 below, we show the minimum detectable differences in HIV testing that can be detected with 80% power under different assumptions of the intra class correlation (ICC) (0.01-0.05), at 5% level of significance, and for different cluster size (number of facilities). For example, if there are 24 facilities in this study (12 in each of the study arms), we will have 80% power to detect a difference of at least 35% in HIV testing when the ICC is 0.01, and at 5% level of significance. Similarly, if we have 18 facilities in this study (9 in each of the study arms), we will have 80% power to detect a difference in HIV testing of at least 45% when the ICC is 0.01, and at 5% level of significance.

These power calculations are based on data on the eligible facilities from the NMM district that show there was an average of 1,687 people tested for HIV in six months per clinic and that average HIV testing was at 14% in this time period.

Significance level	Power	Current proportion of total headcount tested for HIV	Number of clusters	Average cluster size	Coefficient of variation (cv)	ICC	Proportion of headcount tested for HIV needed to achieve 80% power
5% 80%						0.01	0.19
	0.14	12	1687	0.596	0.03	0.23	
						0.05	0.26
5%	80%	0.14	9	1687	0.596	0.01	0.20
						0.03	0.25
						0.05	0.28

Table 4. Assumptions for power calculations, with estimated HIV testing level needed to achieve 80% power.

Statistical analyses

The first three months of the study comprise the "run in" period. Data from the wash-out period will not be used in the analysis. We will use six months of facility data collected during months 4-9 of the intervention for this analysis.

We will employ 'Cluster-level' methods to conduct statistical analysis in a two-stage approach here. The first step will consist of estimating a summary measure for each cluster (facility): we will calculate the % tested for

HIV, % linked to treatment, and % retained in care in each facility for the six months of the intervention period. We will calculate this by aggregating each indicator, then calculating the outcomes of interest (percentages) based on the six-month total counts. In the second step, we will carry out weighted 2-sample t-tests to test the null hypothesis that there is no significant difference between the intervention and the control groups with respect to these summary measures. Weighted approaches are preferred here, as they have been shown to improve efficiency when clusters are not of the same size [24], which is the case in our trial. In our approach, the weights are set to be the inverse of the estimated variance of the cluster summary measures, that is,

$$w_i = \frac{1}{v_i + \sigma^2}$$

where v_i is the variance of the cluster level summary for facility i and σ^2 is the between-cluster (between-facility) variance. We will also conduct additional analyses adjusting for facility-level factors as necessary.

Should changes in testing, linkage to care, and retention in treatment be noted in the analysis, we will descriptively examine these indicators by sex and age groups of interest to understand what demographic was receiving additional testing and/or care as a result of this program. These indicators are available in aggregate in the routinely reported data.

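### Table 4's detectable testing levels match a different test from the planned weighted t-test and use the number tested as cluster size; the net effect is small and conservative

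*Protocol*

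**What the plan says.** Section 7.1 presents Table 4 as the "minimum detectable differences in HIV testing that can be detected with 80% power" for ICCs of 0.01, 0.03 and 0.05. The inputs are 14% tested, an average cluster size of 1,687, a cv of 0.596, and 12 or 9 clinics per arm. The printed levels are 0.19, 0.23 and 0.26 (12 per arm) and 0.20, 0.25 and 0.28 (9 per arm). Two sentences translate the ICC 0.01 cells into relative differences. For 12 per arm, "we will have 80% power to detect a difference of at least 35% in HIV testing when the ICC is 0.01"; for 9 per arm the figure given is 45%. No formula or test is named for these calculations.

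On the cluster size, the text says "there was an average of 1,687 people tested for HIV in six months per clinic". Section 5.1 defines the testing outcome as the number tested divided by head count.

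The Statistical analyses text that follows Table 4 fixes the test: "In the second step, we will carry out weighted 2-sample t-tests to test the null hypothesis". The weights are 1/(v_i + σ²), where v_i is the variance of facility i's summary and σ² the between-facility variance. The reason given is: "Weighted approaches are preferred here, as they have been shown to improve efficiency when clusters are not of the same size".

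**The concern.** The protocol prints both a power table and the test to be run, so the two should belong together. Table 4 lists a cv of cluster size and appears to charge for it in full, while the analysis text picks weights precisely to avoid most of that loss. A t-test on 18-24 facility summaries also has only 16-22 degrees of freedom, which a normal approximation ignores. In addition, one stated input, the cluster size, is the outcome's numerator and not its denominator.

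The number of clinics is set by availability, so Table 4's only job is to say what the trial can detect. A null or borderline testing result will be read against it.

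**Working it through.** **Inputs.** From section 7.1 and Table 4: p0 = 0.14, m = 1,687, cv = 0.596, ICC = 0.01/0.03/0.05, k = 12 or 9 per arm, 5% significance, 80% power. Assumed, because the protocol does not say: a two-sided test, and cv as the coefficient of variation of cluster size.

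**Step 1: reproduce Table 4.** Take the design effect DE = 1 + ICC × (m(1 + cv²) − 1) and an effective size per arm of n = k × m / DE. Here 1 + cv² = 1 + 0.596² = 1.355. For k = 12 and ICC = 0.01, DE = 1 + 0.01 × (1,687 × 1.355 − 1) = 23.85 and n = 12 × 1,687 / 23.85 = 849. Solving the usual two-proportion normal formula (pooled variance under the null) for 80% power gives 0.1905. All six cells:

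| | ICC 0.01 | ICC 0.03 | ICC 0.05 |
|---|---|---|---|
| 12 per arm, computed | 0.1905 | 0.2300 | 0.2591 |
| 12 per arm, printed | 0.19 | 0.23 | 0.26 |
| 9 per arm, computed | 0.1989 | 0.2455 | 0.2800 |
| 9 per arm, printed | 0.20 | 0.25 | 0.28 |

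The other variants tried do not match all six. Without the cv term the levels are 0.183/0.216/0.241 and 0.190/0.229/0.258. With t critical values and the cv term they are 0.193/0.234/0.264 and 0.203/0.252/0.288. With unpooled variance, the 9-per-arm, ICC 0.03 cell is 0.2448 and would round to 0.24. Reading cv as the between-facility variation of the proportion gives 0.31 and 0.38.

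**Step 2: what the planned weights do.** In units of p(1 − p), σ² is the ICC, 0.01 to 0.05, and v_i is about 1/1,687 = 0.0006 at the average size. Between-facility variance is therefore about 17 to 84 times larger, and 1/(v_i + σ²) is nearly constant across facilities. The 1.355 factor on the ICC term belongs to weighting by facility size and does not carry over.

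**Step 3: power of the planned test.** Information per arm is Σ m_i / (1 + (m_i − 1) × ICC), referred to a noncentral t with 2k − 2 df. Cluster sizes are assumed gamma with mean 1,687 and cv 0.596. For k = 12 and ICC = 0.01 the effective size per arm is about 1,106 instead of 849. At 0.186 the standard error is √((0.14 × 0.86 + 0.186 × 0.814) / 1,106) = 0.0157, so the noncentrality is 0.046 / 0.0157 = 2.93, which gives 80% power on 22 df.

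| | ICC 0.01 | ICC 0.03 | ICC 0.05 |
|---|---|---|---|
| 12 per arm, level for 80% power | 0.186 | 0.220 | 0.246 |
| Printed minus this | 0.004 | 0.010 | 0.014 |
| Power at printed level | 86% | 88% | 88% |
| 9 per arm, level for 80% power | 0.195 | 0.236 | 0.266 |
| Printed minus this | 0.005 | 0.014 | 0.014 |
| Power at printed level | 86-87% | 89% | 87% |

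Simulating the weighted t-test on beta-binomial data agrees with these levels to within about 0.002 and gives a type I error of about 5%. The two departures pull in opposite directions: the t reference raises the detectable level by about 0.002-0.008, and the weighting lowers it by about 0.007-0.022.

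**Step 4: cluster size.** On the protocol's own 14%, six-month head count is 1,687 / 0.14 = 12,050. The 30 facilities in Table 1 with a readable head count average 2,049 a month, and 2,049.2 × 6 = 12,295, which agrees. With m = 12,050 the planned test needs 0.184, 0.219 and 0.245 (12 per arm) and 0.193, 0.235 and 0.265 (9 per arm). That moves the Step 3 levels by only about 0.002 or less.

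**Step 5: the worked sentences.** Table 4's cells imply 0.19/0.14 − 1 = 36% and 0.20/0.14 − 1 = 43%; the unrounded 0.1989 gives 42%. The printed 45% matches neither. For the planned test the 80% points at ICC 0.01 are about 33% and 39% with m = 1,687, and about 32% and 38% with head count. At +35% (0.189, 12 per arm) the planned test has about 85% power. At +45% (0.203, 9 per arm) it has about 89%. Both figures are with m = 1,687.

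**The case against.** Sizing on a simple, cautious approximation and then analysing more efficiently is ordinary practice, and the mismatch is inferred, since no formula is stated. Every shift is in the safe direction and at most about 0.015. The protocol's own ICC range moves the level much further, from 0.19 to 0.26 and from 0.20 to 0.28. No decision on enrolment depends on Table 4. All of that stands, and it keeps the point small. It does not make the table describe the planned test, and it does not explain a numerator used as cluster size or a 45% that Table 4 does not yield.

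Three stronger readings are not supported:

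- **That every printed level is wrong.** With m = 1,687, the cell behind the quoted sentence is 0.186 and still prints as 0.19. The 9-per-arm, ICC 0.01 cell is borderline, at 0.194-0.195 against 0.20.
- **That the two worked sentences are false or the trial is underpowered by this mismatch.** Both sentences claim 80% power for differences of at least the stated size, and the planned test exceeds that.
- **That the false-positive rate is inflated.** A naive t-test weighted by facility size would reject about 8% of the time under the null, but the protocol specifies inverse-variance weights, and that test holds about 5%.

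**Conclusion.** The point holds as a minor inconsistency between a stated power figure and the stated test, together with one mislabelled input. On Table 4's other inputs the planned test has about 86-89% power at the printed levels. Five of six levels are too high by about 0.005-0.015 with m = 1,687, and all six shift slightly with head count.

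This rests on the inferred formula, a two-sided 5% test, gamma-distributed cluster sizes and beta-binomial facility proportions. The size distribution matters little because between-facility variance dominates. The 14% base rate matters more: the readable rows of Table 1 give about 12% tested, so the replacement levels are conditional on 14% and on the assumed ICCs.

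**What to change.** In section 7.1:

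1. State the formula behind Table 4 and that the test is two-sided, if it is.
2. Use six-month head count as the cluster size, and label it so.
3. Recompute Table 4 for the planned test: t with 2k − 2 df, facility variance p(1 − p) × ICC plus sampling variance, inverse-variance weights, and no (1 + cv²) factor on the ICC term. On the present 14% and ICCs this gives about 0.18, 0.22 and 0.245 for 12 per arm, and 0.19, 0.235 and 0.265 for 9 per arm. Rerun it if the base rate is revised.
4. Restate the two worked sentences to match, at about 31-32% and 37-38% relative at ICC 0.01.

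If the table is kept, say that its levels are conservative for the planned test, and correct the 45% to agree with the printed 0.20 (43%).

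The cost is one table and two sentences. Enrolment, data and analysis are untouched.

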3.2. Study Location and Population

HIV facilities: This study will primarily be conducted among health facilities in Ngaka Modiri Molema (NMM) district in Northwest Province, for which Aurum is the PEPFAR implementing partner. We selected NMM district because the majority of facilities in this district have not yet participated in Project Unlocked but have expressed interest in the program. There 31 facilities in NMM district currently eligible for this study. These facilities and accompanying details are described in Table 1 (see next page). Project activities will be expanded to facilities in

other districts in Northwest Province if needed for operational reasons or to maintain the power required for this study.

HIV clinics are actively recruited to participate in Project Unlocked. Aurum uses its position as Implementing Partner to identify clinics where additional capacity for non-clinical HIV activities is necessary, and thus identify clinics that could benefit from the Project Unlocked model.

Youth Interns: Project Unlocked passively recruits youth to participate in this project, relying on flyers at community-level health facilities and word of mouth to encourage application to the program. The target youth population for the project is aged 18-30 with low socioeconomic status, minimal education, and limited job experience. The median age of participation is approximately 25 years; youth under 18 are not part of this project. Youth are selected into the program based on the level of need at the HIV clinics in their communities, not based on the youth's skill set or experience.

Table 1. Facilities in NMM district, Northwest Province eligible for inclusion in proposed cluster RCT. Averages were calculated from October 2018-July 2019.

Facility name	Local Municipality	Avg No. Patients / Month	Avg No. Tested/ Month	Avg No. Newly Positive/ Month	Avg No. Initiated/ month	Avg No. Initiated on same day/ month	Total No. On ART (July 2019)	Total No. Default Early (July 2019)
Agisanang Clinic	anang Clinic Tswaing		264	7	7	4	740	76
Bakerville Clinic	Ditsobotla	1075	72	3	4	1	327	67
Blydeville Clinic	Ditsobotla	1244	116	9	8	4	577	99
Blydeville Old	Ditsobotla	1640	209	12	10	5	719	139
Bodibe 1 Clinic	Ditsobotla	3274	501	14	14	10	1181	225
Boikhutso Clinic	Ditsobotla	3907	669	21	20	10	1577	268
Braklaagte	Ramotshere Moiloa	1661	105	5	5	4	536	72
Coligny CHC	Ditsobotla	3033	426	14	14	2	1013	200
Delareyville CHC	Tswaing	2938	416	23	24	17	1331	335

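### The power paragraph's inputs (1,687 tested, 14%) do not match the protocol's own Table 1 (about 1,481, 12.0%), and its 35% and 45% differences are relative figures not labelled as such

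*Protocol*

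**What the plan says.** Section 7.1 of the protocol gives the source of its inputs: "These power calculations are based on data on the eligible facilities from the NMM district". It then reports that "there was an average of 1,687 people tested for HIV in six months per clinic and that average HIV testing was at 14" per cent. Table 4 takes 1,687 as the average cluster size, with a coefficient of variation (cv) of 0.596 and a starting proportion of 0.14. At ICC 0.01 the proportion needed for 80% power is 0.19 with 12 facilities per arm and 0.20 with 9. Further rows cover ICC 0.03 and 0.05.

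The text puts the ICC 0.01 rows into words. For 24 facilities: "we will have 80% power to detect a difference of at least 35% in HIV testing when the ICC is 0.01". For 18: "we will have 80% power to detect a difference in HIV testing of at least 45% when the ICC is 0.01". Neither percentage is described as relative or absolute.

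Three other places bear on this:
- Section 3.2, Table 1, lists the 31 eligible facilities with monthly head count and number tested. Its caption says: "Averages were calculated from October 2018-July 2019".
- Section 5.1 defines the testing outcome as number tested divided by head count.
- The analysis text in section 7.1 plans a weighted two-sample t-test on one summary percentage per facility.

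**The concern.** The power statement claims to rest on the eligible facilities, yet the protocol's own table for them shows fewer people tested and a lower proportion tested. The cluster size is the outcome's numerator, while a calculation for a proportion needs the denominator. The outcome is itself a percentage, so a difference quoted in per cent without a label leaves its scale open.

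With 9 to 12 facilities per arm a null result is quite possible, and readers will judge it against this paragraph. They need to know which difference the trial could detect, on which scale and from which baseline. A relative difference carried from a 14% baseline to a 12% baseline is a smaller absolute difference and has less power.

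**Working it through.** **1. Reproduce Table 4.** Inputs from Table 4: m = 1,687, cv = 0.596, baseline 0.14, two-sided 5% (sidedness is not stated, but two-sided reproduces the table).

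- Design effect = 1 + ((1 + cv²)m − 1) × ICC. At ICC 0.01: 1 + (1.3552 × 1,687 − 1) × 0.01 = 23.85.
- Effective number per arm, 12 facilities: 12 × 1,687 / 23.85 = 849.
- SE for 0.14 against 0.19: √[(0.14 × 0.86 + 0.19 × 0.81) / 849] = 0.0180. Then 0.05 / 0.0180 = 2.78, and power is about 79% with normal quantiles.
- Solving for 80% power gives 0.191, 0.230, 0.259 (12 per arm) and 0.199, 0.246, 0.280 (9 per arm) at ICC 0.01, 0.03, 0.05. All six printed entries match to rounding.

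**2. Recompute the inputs from Table 1.**

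- Number tested, 31 facilities: total 7,653 per month, mean 246.9, so 6 × 246.9 = 1,481 in six months; cv 0.62.
- Proportion tested, 30 facilities (one head count is unreadable in the text available): 7,389 / 61,476 = 12.0%; unweighted mean 11.7%; range 1.9% to 21.3%.
- The unreadable head count cannot close the gap. Its smallest possible value equals the 264 tested there, giving (7,389 + 264) / (61,476 + 264) = 12.4%. For an unweighted mean of 14%, that one facility would have to test about 84% of its head count.
- Head count: mean 2,049 per month, 12,295 in six months, cv 0.47. The protocol's own figures imply much the same: 1,687 / 0.14 = 12,050.
- Between-facility SD of the proportion: 0.0418 (0.0382 without the 1.9% facility). The implied ICC is 0.0418² / (0.12 × 0.88), about 0.017; an ANOVA estimate is about 0.013.

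The printed cv of 0.596 is close to that of number tested (0.62) and not to that of head count (0.47), so it probably describes people tested as well. Using head count and its cv moves the first Table 4 entry only from 0.190 to 0.187, because the ICC term dominates.

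**3. Read the percentages.** 0.19 / 0.14 = +36%, or 5 points. 0.20 / 0.14 = +43%, or 6 points; +45% would be 0.203. Differences of 35 or 45 points would mean 49% or 59% tested, so the text can only mean relative change.

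**4. Power for the planned test on Table 1 data.** Noncentral t on 2k − 2 df with δ = d / (SD√(2/k)), SD 0.0418 in both arms. The standard error is 0.0171 for k = 12 and 0.0197 for k = 9.

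| Facilities | Difference d | δ | Power | Power, SD 0.0382 |
|---|---|---|---|---|
| 24 | 4.2 points (35% of 12%) | 2.46 | 65% | 73% |
| 18 | 5.4 points (45% of 12%) | 2.74 | 73% | 80% |
| 24 | 5.0 points | 2.93 | 80% | 86% |
| 18 | 6.0 points | 3.05 | about 82% | 88% |

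Differences detectable with 80% power: 5.0 points (5.0 / 12 = 42%) with 24 facilities and 5.9 points (5.9 / 12 = 49%) with 18.

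**5. Why the facility SD is the relevant input.** The planned weights are 1/(vᵢ + σ²). Taking vᵢ as binomial, it is about 0.12 × 0.88 / 12,295 = 0.000009 at the average facility, while σ² is about 0.0418² = 0.0017. The weights are therefore nearly equal, and an equal-weight t-test on facility proportions is a close stand-in.

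**6. Sensitivity, 35% rise from 12%, 24 facilities (normal / t).**

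- m = 1,481, cv 0.624, ICC 0.01: 69% / 65%.
- Head count, cv 0.474, ICC 0.01: 76% / 72%.
- Head count, no cv term, ICC 0.013: 73% / 69%.
- Head count, cv term, ICC 0.013: 64% / 60%.
- SD scaling with the mean: 55% / 51%.

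The span is about 51% to 76%. It passes 80% (84% / 81%) only if ICC 0.01, lower than Table 1 shows, is kept and the cv term is also dropped.

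**The case against.** The strongest reply is that the calculation is sound where it matters. Table 4 follows from its inputs and sets out its targets as proportions, 0.14 to 0.19 and 0.14 to 0.20. On that absolute scale the Table 1 SD gives 80% and about 82% power. The figures of 65% and 73% arise only when the text's percentages are moved to a lower baseline. This stands. A reader might infer that the trial has only 65% to 73% power, but the documents do not support that as an unconditional statement.

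Other replies also carry weight:

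- Table 1 averages ten months and section 7.1 speaks of six without dates, so a different window may explain part of the gap. A reader might infer that 1,687 and 14% are wrong; the protocol shows only that they are unreconciled.
- The ICC 0.01 cases are given as examples with the ICC named, and Table 4's range of 0.01 to 0.05 covers the 0.013 to 0.017 seen in Table 1.
- Because Table 4 prints the proportions, a careful reader will not take 35% as points. Quoting 45% where the table implies 43% is also not over-optimistic.
- The number of facilities is fixed by availability, and section 8 lists small size as a limitation.
- Stratifying by HIV testing (section 3.4) may raise power somewhat and is in neither calculation.

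These replies do not answer two things. The stated source and Table 1 disagree. And a relative difference means something definite only with its baseline, which here is in doubt.

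**Conclusion.** The point holds as a fault in inputs and reporting; Table 4's arithmetic is not at fault. Section 7.1 attributes to the eligible facilities a number tested (1,687) and a proportion (14%) that Table 1 does not show (about 1,481 and 12.0%). It uses the outcome's numerator as cluster size, with little numerical effect, and quotes relative differences without saying so.

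Table 4's 5 and 6 points at ICC 0.01 roughly stand. What is not supported is 80% power for rises of 35% and 45% from the Table 1 baseline: about 65% and 73% with the full SD, and 73% and 80% without the lowest facility.

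This assumes that the enrolled 18 to 24 facilities resemble the 30 with readable data, that the SD is equal in both arms, and that stratification and adjustment bring no gain. The support for 5 points is not unconditional either. Putting an ICC of 0.013 to 0.017 into Table 4's formula with the cv term, on head count, lowers power for 5 points with 24 facilities to about 64% to 78%. That approach suits the planned cluster-level test less well, for the reason in step 5.

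**What to change.** Revise Table 4 and the paragraph above it:

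- Reconcile 1,687 and 14% with Table 1, or state the months and facilities from which they come.
- Use head count and its own cv as cluster size (on Table 1, about 12,300 in six months and 0.47).
- Give detectable differences in percentage points, with the relative figure and its baseline in brackets. On Table 1 data with the unadjusted t-test: 5.0 points (about 42% of 12%) with 24 facilities and 5.9 points (about 49%) with 18.
- Name the ICC or between-facility SD behind each figure, and say that the calculation is for a t-test.
- Note that stratification is not counted and may raise power somewhat.

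The cost is one table and one paragraph. The relative differences that can be claimed become somewhat larger. The number of facilities, the design and the analysis stay as they are.
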